4.1 Primary Objectives

The primary objective of the study is to evaluate the improving spontaneous recovery from the clinical deficits at the time of an acute relapse in relapsing remitting multiple sclerosis (RR-MS) patients already receiving interferon (IFN) beta 1a 44mcg TIW with the D-asp (versus placebo) as add-on therapy.

4.2 Secondary Objectives

The secondary objectives of the study are:

- To evaluate the long term recovery in MS related disability following treatment with D-asp;

- To evaluate whether D-asp induces an effect in improving spontaneous recovery of the cognitive functions and fatigue after relapse;
- To evaluate whether D-asp enhances LTP induction, by using transcranial magnetic stimulation (TMS);
- To evaluate whether D-asp is able to influence the immune-phenotype and immune-metabolic response of lymphocytes in MS patients independently by relapse;
- To evaluate the safety and tolerability of D-asp as add-on therapy in RR-MS patients already receiving IFN beta 1a 44mcg TIW.

[figure not shown]
5 Investigational Plan

5.1 Overall Study Design and Plan

This Phase II study will be a prospective, parallel group, double blind, balanced randomised block, placebo-controlled study. The study is expected to start on December 2017 (first patient in) and to end on December 2020 (Clinical Study Report).

The study will be conducted according to the plan presented in Figure 1.

Figure 1. Study plan

Note: the first randomisation (from a specific randomisation list) will involve 10 sites, which will not be involved neither in the immunological analyses nor in TMS; the second randomisation (from a specific randomisation list) will involve only the sites of Rome, Naples and Pozzilli (Isernia), which will collect the blood samples for the immunology analyses, and the third randomisation (from a specific randomisation list) will involve site of Pozzilli for patients without relapse, which will perform the TMS.

The study will be carried out in approximately 18 investigational sites in Italy.

Patients will be recruited from the following 3 MS centres of the 5 Steering Committee members reported in Section 2: PPD

and from other approximately 16 qualified MS centres that will participate to the study.

A number of 120 MS patients presenting with a relapse or not will be randomised to receive either D-asp 2660mg once daily or placebo as add-on to conventional therapies (IFN beta-1a 44mcg TIW for patients without relapse and IFN beta-1a 44mcg TIW plus methylprednisolone i.v. for patients with relapse, for 5 consecutive days at 1000mg once daily).

The TMS will be performed only in the scheduled 40 patients without relapse enrolled in the MS centre of the PI

Immune-phenotype and immune-metabolic response of lymphocytes will be evaluated in 80 patients, which will include 40 patients with relapse enrolled in the sites of Rome, Naples and Pozzilli, and 40 patients without relapse enrolled in the site of Pozzilli. This distribution will allow to measure immunological parameters in a balanced way among patients with D-asp and placebo. Patients that will perform immunological parameters will be randomised separately from those recruited in the other centres (which will enrol only patients with relapse that will be randomised to receive D-asp/placebo and will not perform immunological assessments).

Determinations of immunological parameters will be performed in the laboratory IEOS-CNR in Naples on fresh blood.

The study plan will include five visits in total. An Early Termination (ET) visit will be performed in case of treatment discontinuation.

The patients will be assessed at Screening (Visit -1, Day -5/-3), Baseline (Visit 0, Day 0-Week 0), and at Week 8 (Visit 1), Week 12 (Visit 2) and Week 24 (Visit 3). A \pm 3-day window is allowed for the planned days of the visits.

Clinical assessments and cognitive impairment (EDSS, 25-foot Timed Walk [25WFT]; 9 Hole PEG Test [9HPT]; SDT; Low Contrast Letter Acuity test; MFIS and FSS) will be performed in all patients at screening (Visit -1, Day -5/-3), baseline (Visit 0, Day 0-Week 0), and at Week 8 (Visit 1), Week 12 (Visit 2) and Week 24 (Visit 3) from the first day of treatment with D-asp/placebo, as well as at the ET visit in case of treatment discontinuation. In the case of occurrence of a relapse, clinical assessments will be recorded during the inpatient ward access by neurologist's experts in the diagnosis and treatment of MS.

Neurophysiological assessments (LTP and recruitment curve) will be performed at the centre of the PPD only in patients without relapse, at baseline (Visit 0, Day 0-Week 0), and at Week 8 (Visit 1), Week 12 (Visit 2) and Week 24 (Visit 3) from the first day of treatment with D-asp/placebo, as well as at the ET visit in case of treatment discontinuation.

Immune-phenotype and immunometabolic analysis will be performed in patients enrolled in the centres of Rome, Naples and Pozzilli in samples obtained at baseline (Visit 0, Day 0-Week 0) before receiving corticosteroids, and after 8 (Visit 1) and 12 (Visit 2) weeks from the first day of treatment with D-asp/placebo, as well as at the ET visit in case of treatment discontinuation.

Brain MRI will be performed according to local clinical practice at screening (Visit -1, Day -5/-3), baseline (Visit 0, Day 0-Week 0) or previous MRI will be evaluated if available and 24 (Visit 3) weeks from the first day of treatment with D-asp/placebo, as well as at the ET visit in case of treatment discontinuation, whenever it will be available.

Adherence to treatment will be assessed after 8 (Visit 1), 12 (Visit 2) and 24 (Visit 3) weeks from the first day of treatment with D-asp/placebo, as well as at the ET visit in case of treatment discontinuation.

The occurrence of adverse events (AEs) will be monitored over the total study duration.

Physical examination including recording of vital signs will be performed at screening (Visit -1, Day -5/-3), baseline (Visit 0, Day 0-Week 0), and after 8 (Visit 1), 12 (Visit 2) and 24 (Visit 3) weeks from the first day of treatment with D-asp/placebo, as well as at the ET visit in case of treatment discontinuation.

A serum pregnancy test will be performed in childbearing potential females within 7 days before screening (Visit -1, Day -5/-3). A urine pregnancy test will be performed at baseline (Visit 0, Day 0-Week 0), unless the patient is postmenopausal or surgically sterilized, or if a serum pregnancy test was performed within 7 days before Baseline (Visit 0).

Standard haematology, biochemistry and urine safety tests will be performed according to local clinical practice at screening (Visit -1, Day -5/-3), baseline (Visit 0, Day 0-Week 0), and after 8 (Visit 1), 12 (Visit 2) and 24 (Visit 3) weeks from the first day of treatment with D-asp/placebo, as well as at the ET visit in case of treatment discontinuation.

A standard 12-lead ECG will be performed according to local clinical practice at screening (Visit -1, Day -5/-3) and after 24 (Visit 3) weeks from the first day of treatment with D-asp/placebo, as well as at the ET visit in case of treatment discontinuation.

The duration of the whole study for a patient will be less than 25 weeks, which include 3-5 days of screening period and 24 weeks of treatment period.

5.2 Discussion of Study Design

This Phase II study will be conducted according to a prospective, parallel group, double blind, placebo-controlled study.

The use of a comparative double blind design with the inclusion of a placebo arm is aimed at minimizing the risk of biases in the evaluation of the effects of D-asp. Moreover, the use of a placebo control arm was considered as appropriate for a reliable assessment of the efficacy of the active treatment.

The study is focused on changes in spontaneous recovery after relapse potentially due to D-asp. The expected results of the study are: 1) greater clinical recovery 8 weeks after relapse onset (evaluated as a recovery to the EDSS baseline); 2) enhancement of TMS-induced LTP; and 3) decreased cerebral atrophy in the active treatment group compared to placebo.

The rationale for the study is described in Section 3. A treatment period lasting for 24 weeks is considering adequate for the assessment of the objectives of the study.

The proposed study endpoints are widely accepted as clinically relevant and have been used in numerous clinical studies in patients with RR-MS. The rationale for the *ex-vivo* and *in-vitro*

assessment of the immune-phenotype and immune-metabolic response of lymphocytes is detailed in [Section 3](#).

5.2.1 Inclusion of Special Populations

Not applicable.

5.3 Selection of Study Population

The study will be conducted in 80 consecutive MS patients with relapse in a cohort of RR-MS patients and in 40 RR-MS patients without relapses, both already in treatment with IFN beta-1a 44mcg TIW for at least 6 months and less than 10 years before the screening visit.

Relapse is defined as the occurrence of new or worsening neurological symptoms attributable to MS, which must persist for >24 hours and should not be attributable to confounding clinical factors (e.g., fever, infection, injury, adverse reactions to medications) and immediately preceded by a stable or improving neurological state for least 30 days.

Only persons meeting all the inclusion criteria and none of the exclusion criteria may be enrolled into the study as patients. Prior to performing any study assessments not part of the patient's routine medical care, the Investigator will ensure that the patient or the patient's legal representative has provided written informed consent following the procedure described in [Section 9.2](#).

5.3.1 Inclusion Criteria

All patients (with or without relapse) must fulfil all of the following criteria to be eligible for this study:

- Males and females between 18 and 55 years of age;
- Patients with RRMS, according to the revised McDonald Criteria (2010) (Polman et al, 2011);
- Patients with an expanded disability status scale (EDSS) score between 0 and 3 before screening visit (Kurtzke, 1983) and before relapse (if applicable);
- Patients receiving treatment with IFN beta 1a 44 mcg TIW for at least 6 months but for no more than 10 years before the screening visit;
- Female patients must be neither pregnant nor breastfeeding and must lack childbearing potential as defined by either:
 - Postmenopausal or surgically sterile, or
 - Using a highly effective method of contraception for the duration of the study.

Furthermore, female patients must not have been pregnant from at least three months prior to enter in the study;

- Patients willing and able to comply with the protocol for the total duration of the study;
- Patients able to understand the purposes and the risks of the study;

- Patients have signed the appropriate written informed consent form, approved by the Independent Ethics Committee (IEC), prior to the performance of any study activities.

Patients with relapse must fulfil the additional following criterion to be eligible for this study:

- Deterioration of at least one step in a relevant functional system scale (FSS) (Visual, Brainstem, Pyramidal, Cerebellar and Ambulation score) or an increase in EDSS of 1 point or more compatible, according to physician's judgment, with the therapy prosecution;
- Relapse started within maximum 5 days before the inclusion in the study.

Patients without relapse must fulfil the additional following criterion to be eligible for this study:

- Clinically stable RR-MS.

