8.2 Endpoints

8.2.1 Primary Endpoints

The primary endpoint of the study will be the proportion of patients with recovery in their MS related disability measured at 8 weeks through the Functional Systems Scores of the EDSS (Visual, Brainstem, Pyramidal, Cerebellar, Sensory, Bowel/Bladder and Ambulation score). The subgroup of 40 patients without relapse will not be evaluated for the primary endpoint.

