7 CEREBRAL FUNCTIONS

◦ DEPRESSION AND EUPHORIA

0 **none**

1 **present:** Patient complains of depression or is considered depressed or euphoric by the investigator or significant other.

◦ Depression and Euphoria are documented on the scoring sheet but are not taken into consideration for FS and EDSS calculation.

DECREASE IN MENTATION

0 **none**

1 **signs only:** not apparent to patient and/or significant other

2 **mild:** Patient and/or significant other report mild changes in mentation. Examples include: impaired ability to follow a rapid course of association and in surveying complex matters; impaired judgement in certain demanding situations; capable of handling routine daily activities, but unable to tolerate additional stressors; intermittently symptomatic even to normal levels of stress; reduced performance; tendency toward negligence due to obliviousness or fatigue.

3 **moderate:** definite abnormalities on brief mental status testing, but still oriented to person, place and time

4 **marked:** not oriented in one or two spheres (person, place or time), marked effect on lifestyle

5 **dementia:** confusion and/or complete disorientation

◦ FATIGUE

0 **none**

1 **mild:** does not usually interfere with daily activities

2 **moderate:** interferes, but does not limit daily activities for more than 50 %

3 **severe:** significant limitation in daily activities (> 50 % reduction)

◦ Because fatigue is difficult to evaluate objectively, in some studies it does not contribute to the Cerebral FS score or EDSS step. Please adhere to the study's specific instructions.

FUNCTIONAL SYSTEM SCORE

0 **normal**

1 **signs only in decrease in mentation; mild fatigue**

2 **mild decrease in mentation; moderate or severe fatigue**

3 **moderate decrease in mentation**

4 **marked decrease in mentation**

5 **dementia**

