9 EXPANDED DISABILITY STATUS SCALE

- 0 normal neurological exam (all FS grade 0)
- 1.0 no disability, minimal signs in one FS (one FS grade 1)
- 1.5 no disability, minimal signs in more than one FS (more than one FS grade 1)
- 2.0 minimal disability in one FS (one FS grade 2, others 0 or 1)
- 2.5 minimal disability in two FS (two FS grade 2, others 0 or 1)
- 3.0 moderate disability in one FS (one FS grade 3, others 0 or 1) though fully ambulatory; or mild disability in three or four FS (three/four FS grade 2, others 0 or 1) though fully ambulatory
- 3.5 fully ambulatory but with moderate disability in one FS (one FS grade 3) and mild disability in one or two FS (one/two FS grade 2) and others 0 or 1; or fully ambulatory with two FS grade 3 (others 0 or 1); or fully ambulatory with five FS grade 2 (others 0 or 1)
- 4.0 ambulatory without aid or rest for ≥ 500 meters; up and about some 12 hours a day despite relatively severe disability consisting of one FS grade 4 (others 0 or 1) or combinations of lesser grades exceeding limits of previous steps
- 4.5 ambulatory without aid or rest for ≥ 300 meters; up and about much of the day, characterised by relatively severe disability usually consisting of one FS grade 4 and combination of lesser grades exceeding limits of previous steps
- 5.0 ambulatory without aid or rest for ≥ 200 meters (usual FS equivalents include at least one FS grade 5, or combinations of lesser grades usually exceeding specifications for step 4.5)
- 5.5 ambulatory without aid or rest for ≥ 100 meters
- 6.0 unilateral assistance (cane or crutch) required to walk at least 100 meters with or without resting (see chapter 8, Ambulation)
- 6.5 constant bilateral assistance (canes or crutches) required to walk at least 20 meters without resting (see chapter 8, Ambulation)
- 7.0 unable to walk 5 meters even with aid, essentially restricted to wheelchair; wheels self and transfers alone; up and about in wheelchair some 12 hours a day
- 7.5 unable to take more than a few steps; restricted to wheelchair; may need some help in transferring and in wheeling self
- 8.0 essentially restricted to bed or chair or perambulated in wheelchair, but out of bed most of day; retains many self-care functions; generally has effective use of arms
- 8.5 essentially restricted to bed much of the day; has some effective use of arm(s); retains some self-care functions
- 9.0 helpless bed patient; can communicate and eat

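### The EDSS route into the relapse cohort names no functional system, so a patient can enter on a Cerebral-only worsening that the primary endpoint does not score

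*Combined protocol and SAP*

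**What the plan says.** Section 5.3.1 (and the synopsis) gives two alternative ways into the relapse cohort, joined in one clause: "Visual, Brainstem, Pyramidal, Cerebellar and Ambulation score) or an increase in EDSS of 1 point or more".

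- Score route: "Deterioration of at least one step in a relevant functional system scale (FSS) (Visual, Brainstem, Pyramidal, Cerebellar and Ambulation score".
- EDSS route: "or an increase in EDSS of 1 point or more compatible, according to physician's judgment, with the therapy prosecution". No functional system is named.

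Pre-relapse EDSS must be a "score between 0 and 3 before screening visit (Kurtzke, 1983) and before relapse (if applicable".

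Section 8.2.1 has the primary endpoint "measured at 8 weeks through the Functional Systems Scores of the EDSS (Visual, Brainstem, Pyramidal, Cerebellar, Sensory, Bowel/Bladder and Ambulation score". These seven items are the five of the score route plus Sensory and Bowel/Bladder. Cerebral, system 7 in the Appendix II scoring guide, is not among them.

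The recovery rule is worded in different ways. Section 8.1 and the synopsis speak of getting back to the baseline state within 8 weeks, with disability assessed on the seven scores. Section 5.2 describes the expected result as recovery to the baseline EDSS. No section says whether baseline is the pre-relapse state or the Day 0 visit.

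Appendix II, part 7, gives Cerebral grade 1 for mild fatigue and grade 2 for "mild decrease in mentation; moderate or severe fatigue". It adds that some studies leave fatigue out of the Cerebral score and the EDSS step, and refers the rater to the study's own instructions. The protocol text gives none.

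**The concern.** The EDSS route is open to any system that moves the EDSS, including one that the endpoint leaves out. A patient who enters only because Cerebral worsened has the same seven scores before the relapse and at entry. Such a patient carries no information on whether D-aspartate helps the scored deficits recover, yet is randomised, sits in the ITT set and is counted in the primary comparison.

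Two things are at stake. One is power: non-informative patients pull the two arms together, and the planned size has no margin on the test that reproduces it. The other is interpretation: how these patients are classified depends on a recovery rule that the plan words inconsistently. The 12- and 24-week recovery proportions (section 8.4.3) and the time-to-recovery model (section 8.4.2) inherit the same ambiguity.

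**Working it through.** **1. Can a Cerebral-only change meet the EDSS route?** Use the step table in Appendix II, part 9, with the other systems fixed and ambulation unrestricted. One entry, for EDSS 2.0, reads "minimal disability in one FS (one FS grade 2, others 0 or 1".

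| Pre-relapse state | EDSS before | Cerebral change | EDSS after | Rise |
|---|---|---|---|---|
| all systems 0 | 0 | 0 to 1 | 1.0 | 1.0 |
| one other system at 1 | 1.0 | 0 to 2 | 2.0 | 1.0 |
| two other systems at 1 | 1.5 | 0 to 3 | 3.0 | 1.5 |
| one other system at 2 | 2.0 | 0 to 3 | 3.5 | 1.5 |

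All four start within the permitted 0 to 3 and rise by at least 1 point, and no scored item changes. Fatigue alone can produce the first two if it counts. Grade 3 needs a moderate decrease in mentation.

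**2. What happens to such a patient at Week 8?**

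- Reading A, the seven scores are back at pre-relapse level: met from Day 0, in either arm.
- Reading B, improvement in a scored item: with no scored worsening to reverse, the patient can never recover.
- Reading C, total EDSS is back at pre-relapse level (section 5.2): the Cerebral change must resolve, so the patient is informative and the gap closes.

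**3. The plan's sample size.** Inputs from section 8.1: p1 = 0.40, p2 = 0.70, one-sided alpha 0.05, power 80%, 40 per arm.

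Uncorrected: n = [1.645·√(2·0.55·0.45) + 0.842·√(0.24 + 0.21)]² / 0.30² ≈ 32.9, so 33 per arm.

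Continuity-corrected: n′ = (32.9/4)·[1 + √(1 + 4/(32.9·0.30))]² ≈ 39.3, so 40 per arm, which matches the plan. Exact enumeration of the one-sided continuity-corrected chi-square at 40 per arm gives 79.8% power.

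**4. Dilution.** Let f be the share of relapse patients entering on a Cerebral-only rise. The documents give no value, so every non-zero f below is an assumption.

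Reading A: observed rate = f + (1 − f)·p. At f = 10%, 0.10 + 0.90·0.40 = 46% and 0.10 + 0.90·0.70 = 73%. The difference is (1 − f)·30 points.

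| f | Patients of 80 | Rates | Power, one-sided corrected | n per arm for 80% |
|---|---|---|---|---|
| 0 | 0 | 40% vs 70% | 79.8% | 40 |
| 1% | 0.8 | 40.6% vs 70.3% | 79.0% | – |
| 2.5% | 2 | 41.5% vs 70.8% | 77.8% | 42 |
| 5% | 4 | 43.0% vs 71.5% | 75.9% | 43 |
| 10% | 8 | 46% vs 73% | 71.8% | 47 |

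On the uncorrected one-sided chi-square, power is 85.7% at f = 0 and 79.5% at f = 10%.

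Reading B: observed rate = (1 − f)·p. At f = 10% this is 36% vs 63%, with corrected one-sided power 70.6% and 49 per arm needed. The rates move the other way, but the difference shrinks by the same factor.

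**The case against.** The strongest reply is that the group may be very small. A patient needs a rise of at least 1 EDSS point with no step in any of the seven scores. Section 5.3 also requires new or worsening neurological symptoms attributable to MS, lasting more than 24 hours and not explained by confounders. Fatigue and cognition are measured separately as secondary endpoints, so leaving Cerebral out of the primary endpoint looks deliberate. At f = 1% the power loss is 0.8 points, and on the uncorrected one-sided test even f = 10% leaves power close to 80%. All of this stands. It limits the size but does not remove the route.

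A second reply is that section 8.1 speaks of a relapse associated with worsening in MS-related disability and then assesses disability on the seven scores. That could be read as presupposing a scored worsening. Section 5.3.1 does not impose this, and eligibility is decided there.

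A reader might also infer more than the documents support:

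- **That the visible difference between five entry items and seven endpoint items is the fault.** It is not. All five entry items are scored, and so are Sensory and Bowel/Bladder, so a patient who enters through either has something to recover. Leaving isolated one-step Sensory or Bowel/Bladder changes off the score route is an eligibility choice with no shown harm. Such a change can still qualify: Sensory 0 to 1 with all else 0 moves the EDSS from 0 to 1.0.
- **That these patients certainly count as recovered.** That holds on reading A only.
- **That the gap favours D-aspartate.** Randomisation spreads these patients over both arms, and they are classified alike in each.

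**Conclusion.** The point holds, limited to the Cerebral system. The EDSS route can admit relapse patients with no change in any scored item. On either reading based on the functional scores they are non-informative: always recovered on one, never on the other. Only the total-EDSS reading of section 5.2 closes the gap, so sections 5.2 and 8.2.1 must be reconciled whatever the frequency.

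The consequence is lost power through dilution, not bias. On reading A and the test that reproduces 40 per arm, the loss is 2.0 points at f = 2.5% (79.8% to 77.8%) and 8.0 points at f = 10% (79.8% to 71.8%). These figures rest on the plan's 40% and 70% applying to the patients who do have a scored deficit, and on an assumed f. If f is near zero, little power is lost and what remains is a gap in definition. The change is still worth making, because it is cheap and settles how such patients are classified.

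**What to change.** Keep both entry routes and make three changes.

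1. In section 5.3.1 and the synopsis, require a patient entering by the EDSS route to have a documented worsening of at least one step from the pre-relapse level in at least one of the seven endpoint-scored items. Record which items worsened. Do not widen the score route to isolated one-step Sensory or Bowel/Bladder changes, since that would alter the relapse population.
2. Define recovery once, as return of the worsened scored items to their pre-relapse level. Use that definition in sections 8.1, 8.2.1 and 8.2.2, and reconcile the baseline-EDSS wording in section 5.2 with it.
3. State whether fatigue counts in the Cerebral score and the EDSS step, as Appendix II asks each study to do.

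The cost is a short eligibility clarification and one added e-CRF field. A few patients with isolated Cerebral worsening would no longer qualify for the relapse cohort.
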